10.5 Prior and Concomitant Medications/Therapies

Restrictions related to use of OAB treatments prior to enrollment in the study is outlined in the study-specific exclusion criteria. Subjects will be prohibited from taking overactive bladder medications and starting any additional advanced therapies for OAB during the first 12 months of their study participation. If the subject is consented while taking overactive bladder medications, they must have a washout of 2 weeks prior to starting the baseline voiding diary and the baseline Overactive Bladder Quality of Life Questionnaire (OAB-q). Any overactive bladder medications will be captured on a study-specific medication log, and any new advanced therapies for OAB will be captured within the follow-up visit. If additional treatment is added prior to the 12-month follow-up visit, a protocol deviation is required. Throughout the study, a voiding diary is required prior to starting any OAB medication or advanced therapies to confirm the patient is a non-responder (< 50% improvement from baseline) to tibial neuromodulation therapy. If additional treatment is added without confirmation of non-response to the therapy documented on a voiding diary, a deviation is required.

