14.1.1 Analysis Sets

All Enrolled analysis set: Includes subjects who completed the informed consent process.

Full Analysis Set (FAS): Includes subjects with an attempted implant. If all implant procedures are successful, this will be equivalent to the All Implanted Analysis set.

All Implanted Analysis set: Includes subjects who are implanted.

Complete Case analysis sets: Includes subjects who are implanted and provide outcome measures at both baseline and follow-up visits. This set is defined for each outcome measure at each follow-up visit.

The study requires subjects to have UUI to be implanted. UUI subjects are those who have ≥ 1 urinary urge incontinence episode per day at baseline. For analysis purposes, Urinary Frequency (UF) subjects are those who have ≥ 10 urinary frequency episodes per day at baseline and all subjects will be considered to have urinary urgency since all eligible subjects have UUI. Some supportive, secondary objective, and additional measure analyses may use different definitions or subsets of the analysis sets listed above (e.g., changed assumptions for those subjects considered to have either UUI or UF).

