Additional supporting analyses to further understand the primary objective will be completed through analyses of the change in UUI (secondary objective) and percentage change in UUI (additional measure).

To assess the robustness of the primary objective results under the influence of missing data, sensitivity and subgroup analyses will be conducted using alternative missing data methods and by including different subsets of subjects. The first sensitivity analysis will be completed including subjects from the Primary Objective Complete Case analysis set. This analysis set will be used for a second sensitivity analysis which will be completed including only subjects who received stimulation ('As treated analysis') at the 6-month follow-up visit. An analysis will also be completed to evaluate UUI responder rate differences between different programs. A tipping point sensitivity analysis will also be completed. A final sensitivity analysis will be conducted on the Primary Objective Complete Case analysis set assigning response failure for all subjects who took OAB medication or received an advanced therapy from implant to the 6-month follow-up visit.

Complete Case analysis set subgroup analyses will be done for the following subject groups: sex, age (divided by median age; divided by age 65), race, and ethnicity. Subjects on the demographic cut point will be added to the adjacent group containing fewer subjects. Any subgroup with less than 10 subjects will not be reported.

As an exploratory analysis to assess if treatment effect differs by study center, a supporting analysis will be completed, as described in 14.1.4. This analysis will test whether the treatment effect is homogeneous between study centers for the UUI responder rate at 6 months.

UUI responder rate will be assessed over time through 24 months as part of the additional measures.

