14.7 Sample Size Determination

The sample size for the primary objective was estimated using a binomial distribution for a one-sided alpha=0.025 test to show a 15% increase for the proportion compared to a performance goal of 40%. Assuming the alternative hypothesis of $\geq 55\%$ of subjects who are considered an UUI responder, a minimum of 121 implant attempted subjects achieves at least 90% power to reject a performance goal of 40%. The primary objective will have at least 88% power for any alternative hypothesis that is at least 15% larger than a performance goal. Secondary objectives are also expected to be adequately powered based on this sample size.

Assuming a $\sim 40\%$ attrition rate before implant, up to 200 subjects will be consented to achieve at least 121 subjects with implant attempted. Enrollment will be closed once the number of completed implants reaches 121; all enrolled subjects who meet eligibility criteria may be implanted (not to exceed 130 total implants). Implant attempted subjects who exit from the study will not be replaced.

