**Supportive and Sensitivity Analyses:** There are no requirements or expectations for the results of the supporting and sensitivity analyses. They are meant to investigate the robustness of the study results and/or to provide further details on the therapy effects.

Additional supporting analyses to further understand the primary objective will be completed through analyses of the change in UUI (secondary objective) and percentage change in UUI (additional measure).

To assess the robustness of the primary objective results under the influence of missing data, sensitivity and subgroup analyses will be conducted using alternative missing data methods and by including different subsets of subjects. The first sensitivity analysis will be completed including subjects from the Primary Objective Complete Case analysis set. This analysis set will be used for a second sensitivity analysis which will be completed including only subjects who received stimulation ('As treated analysis') at the 6-month follow-up visit. An analysis will also be completed to evaluate UUI responder rate differences between different stimulation programs, comparing stimulation programs only if there are an adequate number of subjects in each stimulation program to ensure a stable estimate of response. A tipping point sensitivity analysis will also be completed. A final sensitivity analysis will be conducted on the Primary Objective Complete Case analysis set assigning response failure for the following subjects: those who took any dose of OAB medication in the 2 weeks prior to the diary collection period, and those who received an advanced therapy at any time from implant to the 6-month follow-up visit.

Complete Case analysis set subgroup analyses will be done for the following subject groups: sex, age (divided by median age; divided by age 65), race, and ethnicity. Subjects on the demographic cut point will be added to the adjacent group containing fewer subjects. Any subgroup with less than 10 subjects will not be reported.

As an exploratory analysis to assess if treatment effect differs by study center, a supporting analysis will be completed, as described in 7.3. This analysis will test whether the treatment effect is homogeneous between study centers for the UUI responder rate at 6 months.

UUI responder rate will be assessed over time through 24 months as part of the additional measures.

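### The sensitivity analysis that scores added OAB treatment as failure uses complete cases only, so subjects with recorded added treatment and no month-6 diary are dropped and this supportive check reads too high

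*Protocol*

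**What the plan says.** The primary endpoint is a reduction of at least 50% in daily UUI episodes at 6 months, tested against 40%. Among the sensitivity analyses, CIP 14.4.1 states: "A final sensitivity analysis will be conducted on the Primary Objective Complete Case analysis set assigning response failure for all subjects who took OAB medication"; receipt of an advanced therapy also counts, and the period runs from implant to the 6-month visit. SAP 7.9.1.1 keeps the set: "A final sensitivity analysis will be conducted on the Primary Objective Complete Case analysis set assigning response failure for the following subjects". It then narrows the medication criterion to any dose in the 2 weeks before the diary period, while advanced therapy still counts at any time from implant to month 6.

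The Complete Case set is defined in CIP 14.1.1 (and likewise in SAP 7.1.3): "Includes subjects who are implanted and provide outcome measures at both baseline and follow-up visits". A diary shorter than 48 hours counts as missing (CIP 14.1.2, SAP 7.4).

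Other provisions that bear on the point:

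- OAB medication and new advanced therapies are barred for the first 12 months, and adding them is a deviation. CIP 10.5 also says that "a voiding diary is required prior to starting any OAB medication or advanced therapies to confirm the patient is a non-responder", meaning less than 50% improvement. Medication goes on a study log; new advanced therapies are recorded at follow-up.
- A subject explanted without replacement is exited (CIP 6, 10.14.1), and no study data are collected after exit (CIP 10.14.1). CIP 10.14 foresees explanted subjects seeking other OAB treatment.
- With 5% or less missing, the primary analysis is itself complete case; above that, multiple imputation is applied to the Full Analysis Set.
- A tipping point analysis is planned, without a described method.

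**The concern.** A rule that scores added treatment as failure does not need a month-6 diary to classify the subject; the treatment record is enough. Tying the rule to the Complete Case set reintroduces the diary requirement and removes the subjects for whom the rule adds most: those who turned to other treatment and then left, were explanted or missed the diary. The CIP wording covers all subjects who took medication, but the chosen set excludes some of them and no sentence brings them back.

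At stake is the usefulness of the only readable 6-month analysis that counts added treatment as failure. It is presented as a robustness check, and dropping scored failures can only move its estimate upwards. In a borderline trial it could look reassuring when the same rule applied to everyone would not.

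**Working it through.** **Inputs.** Performance goal 0.40, one-sided alpha 0.025, N=121 implant-attempted subjects and alternative 0.55 (CIP 14.7, SAP 6). The number k of subjects with recorded added treatment and no usable month-6 diary is not in the documents; I assume 0 to 12 (0% to 10% of 121) and treat every other subject as observed.

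**Step 1: the plan's own figures.** Exact binomial: P(X≥59 | 121, 0.40)=0.0313 and P(X≥60 | 121, 0.40)=0.0204, so 60 responders (49.6%) are needed. Power is P(X≥60 | 121, 0.55)=0.901, which reproduces the stated 90%. The companion statement of at least 88% also reproduces: over goals from 0.05 to 0.79 with an alternative 0.15 higher, the lowest exact power at N=121 is 0.882.

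**Step 2: size of the shift.** With r responders, the planned check reports r/(121-k). With the k subjects kept as failures it is r/121. The ratio is 121/(121-k), above 1 whenever k>0.

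**Step 3: effect near the boundary.** The fourth column is what the planned check is expected to read if the full-set rate is exactly 40%, that is 48.4/(121-k). The last column is the chance that it then shows one-sided p≤0.025, taking r as binomial on 121-k with that rate.

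| k | n used | factor | reads | responders needed | verdicts differ for r = | chance of nominal significance |
|---|---|---|---|---|---|---|
| 2 | 119 | 1.017 | 40.7% | 59 | 59 | 3.0% |
| 4 | 117 | 1.034 | 41.4% | 58 | 58-59 | 4.5% |
| 6 | 115 | 1.052 | 42.1% | 57 | 57-59 | 6.4% |
| 10 | 111 | 1.090 | 43.6% | 56 | 56-59 | 8.7% |
| 12 | 109 | 1.110 | 44.4% | 55 | 55-59 | 12.0% |

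With the k subjects retained, the requirement stays at 60 of 121 and the corresponding chance is 1.6% to 2.0%. With k=0 or k=1 the two verdicts never differ.

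**Step 4: examples.**

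- k=6, r=57: 57/115=49.6%, p=0.0236; 57/121=47.1%, p=0.0672.
- k=2, r=59: 59/119=49.6%, p=0.0214; 59/121=48.8%, p=0.0313.
- k=6, r=66: 66/115=57.4%, p=0.0001; 66/121=54.5%, p=0.0009. Both pass.

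If the full-set rate is 55% (rate among those observed 66.55/(121-k)), the chance of landing where the verdicts differ is 2.8% for k=2 and 6.3% for k=6.

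**Step 5: the two medication rules.** The CIP counts medication at any time from implant to month 6, so a subject without a diary can be classified. The SAP window runs backwards from the diary, so without a month-6 diary it has no anchor. Advanced therapy does not have this problem in either document.

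**The case against.** The strongest case on the other side has five parts.

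- **The check decides nothing.** CIP 14.4.1 and SAP 7.9.1.1 attach no requirement to sensitivity analyses, and success rests on the primary test (CIP 14.1). This stands. A reader might infer that the trial's type I error is inflated or that the primary result is biased. The documents do not support that: the primary endpoint does not score added treatment as failure, and the percentages in the table's last column describe a supportive check, not an alpha-controlled test.
- **The group may be small or empty.** Added treatment is prohibited to month 12, so k counts only deviations that were recorded and were followed by a missing diary. Treatment begun after exit is not collected. This stands, and the size remains an assumption.
- **Failure is not observed at month 6.** One might say these subjects are known month-6 failures. They are not: the diary required before adding treatment shows non-response at that time, and the CIP foresees treatment added without it. Failure is the convention of this analysis. The point is that the convention is not applied to everyone it covers.
- **The SAP medication rule is narrower.** A subject who took medication early and left is not a failure under the SAP as written. This stands, and the remedy must deal with it.
- **Other analyses address missing diaries.** The tipping point analysis and, above 5% missing, multiple imputation do so in part. Both treat these subjects as ordinary missing data, and imputation can make them responders. At 6 of 121 (4.96%), with no other losses, the primary analysis is itself complete case, so the same subjects are absent from both.

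**Conclusion.** The point holds as a limited one. Both documents restrict the added-treatment check to complete cases, which biases that check upwards by 121/(121-k) relative to the same rule applied to all implant-attempted subjects. At an assumed k=6, that is 2.1 points at a full-set rate of 40% (42.1% against 40%) and 2.6 points at 50% (0.50 × 121/115 = 52.6%). The check's verdict changes only for borderline counts: 59 responders at k=2, 57 to 59 at k=6. A clear result at the planning rate is not disturbed.

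This rests on k being above zero, which the documents neither state nor exclude, and on all other subjects being observed. For medication under the SAP, it also rests on a window that is not yet defined for subjects without a diary. It is worth correcting because the change is cheap and a robustness check matters most when the result is close.

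**What to change.** In CIP 14.4.1 and SAP 7.9.1.1:

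1. Run this analysis on the Full Analysis Set.
2. Score as failure every implant-attempted subject with recorded advanced therapy from implant to month 6, or with recorded OAB medication under the analysis rule, whether or not a month-6 diary exists.
3. Apply the planned multiple imputation only to the remaining subjects without a diary.
4. Reconcile the two medication rules (any time from implant in the CIP, 2 weeks before the diary in the SAP). If a diary-based window is kept, define it for subjects without a month-6 diary, for example anchored to the exit date or the target visit date.

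The cost is wording in two documents, including one new definition, and no new data collection. The sensitivity estimate may come out slightly lower. Treatment started after study exit would still not be captured, and the text should say so.

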14.5 Secondary Objective(s)

The following secondary objectives have specific hypotheses to be tested. After the primary objective is met, these four secondary objectives will be tested as described in 14.1.3.

14.5.1 Secondary Objective – UUI Change

To demonstrate an improvement from baseline to 6 months in number of UUI episodes in subjects with UUI at baseline

Hypothesis: The change from baseline in UUI episodes is not 0.

$$H_0: \mu = 0$$

$$H_A: \mu \neq 0$$

Where μ = the change in UUI episodes

Endpoint Definition and Derivation: A 3-day urinary voiding diary will be used to collect bladder symptoms, including UUI episodes. Calculation of change in UUI is defined in the voiding diary analysis section 14.1.5. A negative change in UUI episodes represents an improvement.

Performance Requirements: The null hypothesis will be rejected if the two-sided p-value is determined to be significant, as described in section 14.1.3.

Sample Size Justification: Data from published studies or studies presented at conferences on TNM outcomes at 3, 6, and 9 months were used as starting points to estimate expected reduction in UUI episodes as well as expected patient-to-patient variability. Assumption on the expected mean difference (-2.0 episodes per day) and standard deviation (3.5 episodes per day) was used to assess statistical power. Presuming a two-sided, one-sample t-test with alphas ranging from 0.013 to 0.05, power is calculated to be no less than 99% for any of the scenarios examined with a sample size of 121 subjects. Additionally, the minimum detectable change in mean episodes was calculated to be as low as -1.0.

Analysis Methods: The analysis for change in UUI will be summarized for baseline, at 6 months after implant, and for the change from baseline. If 5% of the data or fewer are missing for the analysis, no imputation will be used, and the objective will be tested using a paired t-test following the multiple testing strategy described in section 14.1.3. If more than 5% of the data are missing, missing data will be imputed as specified in section 14.1.2. If non-normality of the data is detected via a significant ($p < 0.05$) Shapiro-Wilk test, a Wilcoxon signed-rank test will replace the t-test.

Determination of Subjects/Data for Analysis: The change in UUI analysis will include all subjects from the Full Analysis Set (i.e., all implant attempted subjects) as defined in section 14.1.1.

Supportive and Sensitivity Analyses: There are no requirements or expectations for the results of the supporting and sensitivity analyses.

Additional supporting analyses to further understand the UUI secondary objective will be completed through analyses of the percentage change in UUI (additional measure).

To assess the robustness of the objective results under the influence of missing data, sensitivity analyses will be conducted using alternative missing data methods. The first sensitivity analysis will be completed including subjects from the Secondary Objective (UUI Change) Complete Case analysis set. This analysis set will be used for a second sensitivity analysis which will be completed including only subjects who received stimulation ('As treated analysis') at the 6-month follow-up visit. A final complete case sensitivity analysis will be performed comparing the change in UUI episodes to a performance goal of 1 episode/day.

UUI change from baseline will be assessed over time through 24-months as part of the additional measures.

14.5.2 Secondary Objective – UF Change

To demonstrate an improvement from baseline to 6 months in number of UF episodes in subjects with UF at baseline

Hypothesis: The change from baseline in UF episodes is not 0.

$$H_0: \mu = 0$$

$$H_A: \mu \neq 0$$

Where μ = the change in UF episodes

Endpoint Definition and Derivation: A 3-day urinary voiding diary will be used to collect bladder symptoms, including UF episodes. UF episodes include all urinary voids. Calculation of change in UF is defined in the voiding diary analysis section 14.1.5. A negative change in UF episodes represents an improvement.

Performance Requirements: The null hypothesis will be rejected if the two-sided p-value is less than 0.05.

Sample Size Justification: Data from published studies on TNM outcomes at 6 months were used as a starting point to estimate expected reduction in UF episodes as well as expected patient-to-patient variability. Assumption on the expected mean difference (-2.0 episodes per day) and standard deviations (3.0 episodes per day) were used to assess statistical power. Presuming a two-sided, one-sample t-test with alphas ranging from 0.013 to 0.05, power is calculated to be no less than 98% for any of the scenarios examined with a sample size of 51 subjects (as only 42% of the total 121 subjects in the study are expected to have UF with 10 episodes per day at baseline). Additionally, the minimum detectable difference in mean daily episodes was calculated to be as low as 1.4.

Rationale for Clinical Relevance: No published data are available defining minimum clinically meaningful improvement for the change in UF episodes. In the absence of published definitions, assessment of effect size can be used to determine the level of effect. As published by Cohen (1988)²⁷, an effect size of 0.2 indicates a small effect, 0.5 a modest effect, and 0.8 a large effect. A modest effect size would correspond to a change of -1.5 episodes per day. The assumed mean \pm standard deviation difference of 2.0 ± 3.0 UF episodes per day (i.e., an effect size = 0.67) for implantable tibial therapy is considered a medium to large effect.

Analysis Methods: The analysis for change in UF will be summarized for baseline, at 6 months after implant, and for the change from baseline. If 5% of the data or fewer are missing for the analysis, no imputation will be used, and the objective will be tested using a paired t-test following the multiple testing strategy described in section 14.1.3. If more than 5% of the data are missing, missing data will be imputed as specified in section 14.1.2. If non-normality of the data is detected via a significant ($p<0.05$) Shapiro-Wilk test, a Wilcoxon signed-rank test will replace the t-test.

Determination of Subjects/Data for Analysis: The change in UF analysis will include all subjects from the Full Analysis Set (i.e., all implant attempted subjects) who have UF as defined in section 14.1.1.

Supportive and Sensitivity Analyses: There are no requirements or expectations for the results of the supporting and sensitivity analyses.

To assess the robustness of the objective results under the influence of missing data, sensitivity analyses will be conducted using alternative missing data methods. The first sensitivity analysis will be completed including subjects from the Secondary Objective (UF Change) Complete Case analysis set. This analysis set will be used for a second sensitivity analysis which will be completed including only subjects who received stimulation ('As treated analysis') at the 6-month follow-up visit. A final complete case sensitivity analysis will be performed comparing the change in UF episodes to a performance goal of 1 episode/day. A Complete Case supporting analysis will be provided assessing the UF change from baseline using different definitions of UF (UF defined as ≥ 8 and UF defined as ≥ 12).

UF change from baseline will be assessed over time through 24 months as part of the additional measures.

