14.1.3 Multiplicity Adjustments

The primary objective is the percentage of subjects considered a UUI responder at 6 months. Four secondary objectives will also be assessed, all of which will be assessed 6 months after implantation of tibial neuromodulation.

To support an indication for OAB, device effectiveness will be demonstrated for the symptoms associated with OAB, including UUI, UF, and urgency. UUI therapy effectiveness will be demonstrated if the primary objective proportion of subjects with UUI response is greater than the performance goal (40%). UF therapy effectiveness will be demonstrated if the secondary UF objective demonstrates an

improvement from baseline to 6 months in number of UF episodes. Urgency therapy effectiveness will be demonstrated if the secondary urgency objective demonstrates an improvement from baseline to 6 months in urinary urgency.

The p-values for the primary and secondary objectives will be calculated according to the methods outlined in their respective analysis sections. The p-values will be reported unadjusted and two-sided; however, declarations of statistical significance will follow the procedures laid out in this section.

The primary objective will be tested separately from the secondary objectives. If the one-sided primary objective p-value is <0.025 , then the null hypothesis will be rejected, and the test will be declared statistically significant.

The Hochberg method for the multiplicity adjustment will be used to test the four secondary objective hypotheses, thereby maintaining an overall two-sided type I error rate at 0.05 for these objectives. Each p-value for the four secondary objectives will be calculated. If all p-values are less than 0.05 (two sided), all will be declared significant. If not, the p-values will be ordered from largest to smallest (identified as p1-p4 in this section). If p1 is greater than 0.05, the remaining p-values (p2, p3, p4) will be compared against an alpha of 0.025 (0.05/2). If the three remaining p-values are all less than 0.025, they will all be declared significant. If p2 is greater than 0.025, the remaining p-values (p3, p4) will be compared against an alpha of 0.017 (0.05/3). If p3 and p4 are both less than 0.017, they will both be declared significant. If p3 is greater than 0.017, p4 will be compared against an alpha of 0.013 (0.05/4). If p4 is less than 0.013, it will be declared significant.

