## 7.5 Adjustments for Multiple Comparisons

The primary objective is the percentage of subjects considered a UUI responder at 6 months. Four secondary objectives will also be assessed, all of which will be assessed 6 months after implantation of tibial neuromodulation.

To support an indication for OAB, device effectiveness will be demonstrated for all the symptoms associated with OAB, including UUI, UF, and urgency. UUI therapy effectiveness will be demonstrated if the primary objective proportion of subjects with UUI response is greater than the performance goal (40%). UF therapy effectiveness will be demonstrated if the secondary UF objective demonstrates an improvement from baseline to 6 months in number of UF episodes. Urgency therapy effectiveness will be demonstrated if the secondary urgency objective demonstrates an improvement from baseline to 6 months in UU.

The p-values for the primary and secondary objectives will be calculated according to the methods outlined in their respective analysis sections. The p-values will be reported unadjusted and two-sided; however, declarations of statistical significance will follow the procedures laid out in this section.

The primary objective will be tested separately from the secondary objectives. If the one-sided primary objective p-value is <0.025, then the null hypothesis will be rejected, and the test will be declared statistically significant.

The Hochberg method for the multiplicity adjustment will be used to test the four secondary objective hypotheses, thereby maintaining an overall two-sided type I error rate at 0.05 for these objectives. Each p-value for the four secondary objectives will be calculated. If all p-values are less than 0.05 (two sided), all will be declared significant. If not, the p-values will be ordered from largest to smallest (identified as p1-p4 in this section). If p1 is greater than 0.05, the remaining p-values (p2, p3, p4) will be compared against an alpha of 0.025 (0.05/2). If the three remaining p-values are all less than 0.025, they will all be declared significant. If p2 is greater than 0.025, the remaining p-values (p3, p4) will be compared against an alpha of 0.017 (0.05/3). If p3 and p4 are both less than 0.017, they will both be declared significant. If p3 is greater than 0.017, p4 will be compared against an alpha of 0.013 (0.05/4). If p4 is less than 0.013, it will be declared significant.

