### 7.9.2.2 Secondary Objective – UF Change

To demonstrate an improvement from baseline to 6 months in number of UF episodes in subjects with UF at baseline

**Hypothesis:** The change from baseline in UF episodes is not 0.

$$H_0: \mu = 0$$

$$H_A: \mu \neq 0$$

Where  $\mu$  = the change in UF episodes

**Endpoint Definition and Derivation:** A 3-day urinary voiding diary will be used to collect bladder symptoms, including UF episodes. UF episodes include all urinary voids. Calculation of change in UF is defined in the voiding diary analysis section 7.2.2. A negative change in UF episodes represents an improvement.

**Performance Requirements:** The null hypothesis will be rejected if the two-sided p-value is determined to be significant, as described in section 7.5.

**Sample Size Justification:** Data from published studies on TNM outcomes at 6 months were used as a starting point to estimate expected reduction in UF episodes as well as expected patient-to-patient variability. Assumption on the expected mean difference (-2.0 episodes per day) and standard deviations (3.0 episodes per day) were used to assess statistical power. Presuming a two-sided, one-sample t-test with alphas ranging from 0.013 to 0.05, power is calculated to be no less than 98% for any of the scenarios examined with a sample size of 51 subjects (as only 42% of the total 121 subjects in the study are expected to have UF with 10 episodes per day at baseline). Additionally, the minimum detectable difference in mean daily episodes was calculated to be as low as 1.4.

**Rationale for Clinical Relevance:** No published data are available defining minimum clinically meaningful improvement for the change in UF episodes. In the absence of published definitions, assessment of effect size can be used to determine the level of effect. As published by Cohen (1988), an effect size of 0.2 indicates a small effect, 0.5 a modest effect, and 0.8 a large effect. A modest effect size would correspond to a change of -1.5 episodes per day. The assumed mean  $\pm$  standard deviation difference of  $2.0 \pm 3.0$  UF episodes per day (i.e., an effect size = 0.67) for implantable tibial therapy is considered a medium to large effect.

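### Protocol 14.5.2 rejects the UF null at an unadjusted two-sided 0.05, although Hochberg governs UF elsewhere in both documents: a leftover sentence to correct

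*Protocol*

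**What the plan says.** Protocol 14.5.2, Performance Requirements, gives the UF decision rule as "The null hypothesis will be rejected if the two-sided p-value is less than 0.05", with no reference to multiplicity. The other places that set a rule for UF say something different:

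- Protocol 14.1.3 puts all four secondary objectives under Hochberg at an overall two-sided 0.05 and adds that "declarations of statistical significance will follow the procedures laid out in this section".
- Protocol 14.5: "After the primary objective is met, these four secondary objectives will be tested as described in 14.1.3".
- Protocol 14.5.2, Analysis Methods, on UF itself: "the objective will be tested using a paired t-test following the multiple testing strategy described in section 14.1.3".
- SAP 7.9.2.2, on UF: "The null hypothesis will be rejected if the two-sided p-value is determined to be significant, as described in section 7.5".

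For the UUI change objective, protocol 14.5.1 has "The null hypothesis will be rejected if the two-sided p-value is determined to be significant, as described in section 14.1.3", and 14.5.3 and 14.5.4 repeat it for UPS and OAB-q. The UF sentence matches the one in protocol 14.4.1 for the primary objective, where it is in place because the primary is tested on its own.

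On the cut-offs, protocol 14.1.3 and SAP 7.5 show 0.05/3 and 0.05/4 in brackets when each level is introduced. The sentences that then declare significance use only 0.017 and 0.013.

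**The concern.** Section 14.5.2 holds two decision rules for one hypothesis, and they can give opposite answers. Take UF p = 0.03, one other secondary at 0.20 and the other two below 0.001. The Performance Requirements sentence rejects the UF null. Hochberg does not: 0.20 fails at 0.05, and 0.03 then fails at 0.025.

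UF is not a peripheral endpoint. SAP 7.5, like protocol 14.1.3, ties it to the OAB indication: "UF therapy effectiveness will be demonstrated if the secondary UF objective demonstrates an improvement from baseline to 6 months in number of UF episodes". Its rejection rule should therefore read the same in every place. Both documents also claim control of the secondary family at two-sided 0.05, which the literal sentence would not deliver.

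**Working it through.** **1. Reproduce the plan's UF power.** Protocol 14.5.2: "Assumption on the expected mean difference (-2.0 episodes per day) and standard deviations (3.0 episodes per day) were used to assess statistical power", with n = 51 and alphas from 0.013 to 0.05. For a two-sided one-sample t-test with 50 df, the noncentrality is (2.0/3.0) × √51 = 4.76.

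| Alpha | UF power |
|---|---|
| 0.05 | 99.66% |
| 0.025 | 99.18% |
| 0.05/3 | 98.71% |
| 0.013 | 98.33% |
| 0.0125 | 98.27% |

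The stated minimum of 98% is reproduced, and it holds at the exact cut-off 0.0125.

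**2. Where the rules differ.** If all four p-values are below 0.05, Hochberg rejects all four and the rules agree. They can differ only when another secondary exceeds 0.05. If exactly one does and the other two are below 0.025, they differ for UF p from 0.025 to 0.05. In observed mean fall (critical t × 3.0/√51) that is 0.84 to 0.97 voids per day.

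**3. Chance of disagreement at the planned effects.** P(0.025 < UF p < 0.05) = 0.9966 − 0.9918 = 0.005. Disagreement also needs another secondary to miss 0.05. UUI (mean 2.0, SD 3.5, n = 121) has power of about 0.99999 at 0.05, and UPS and OAB-q have more. The chance that any of the three misses is therefore about 0.00001, which caps the disagreement probability whatever the correlation. Under independence, this window contributes about 0.005 × 0.00001 = 5 in 100 million.

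**4. Family-wise error if the 0.05 sentence were applied and UF were a true null.** Set the p-values of non-null secondaries to zero. Under independence:

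- UF the only null: 0.05, no excess.
- Two nulls: 0.05 + 0.95 × 0.025 = 0.074.
- Three nulls: given UF p above 0.05, Hochberg rejects one of the other two nulls if the smaller p is below 0.05/3 or both are below 0.025. That probability is 1 − (1 − 0.05/3)² + (0.025 − 0.05/3)² = 0.0331. The total is 0.05 + 0.95 × 0.0331 = 0.081.

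Exact Hochberg with three independent nulls gives 0.049 by simulation.

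**5. Effect of correlation.** The documents give no correlations, so these are assumptions. UF uses 51 subjects and the other tests use 121. With equal subject-level variances in the UF subset and the rest, the UF statistic correlates with the others at no more than √(51/121) = 0.65. Simulation with three nulls, all pairwise correlations 0.65, gives about 0.07.

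**6. Rounding.** 0.05/3 = 0.01667 and 0.05/4 = 0.0125, so the printed values are high by 0.00033 and 0.0005. For example, p-values of 0.06, 0.03, 0.02 and 0.0128 give one rejection at 0.013 and none at 0.0125. Simulated family-wise error with printed against exact cut-offs is 5.1% against 4.9% with four independent nulls and 5.03% against 4.93% with three. There is no change with one or two. At an assumed correlation of 0.25 the four-null figure is already below 5% (4.96%).

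**The case against.** The strongest reply is that the documents already settle the matter. Protocol 14.1.3 takes p-values from the objective sections but reserves declarations of significance to itself, which works as a precedence rule. Protocol section 14 describes itself as high-level and leaves detail to the SAP, and the SAP's UF sentence is correct. All of this stands, and it is why the point is small. It does not make the sentence harmless: it sits in the paragraph that states the rejection rule, for an endpoint that carries part of the indication.

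A reader might infer more than the documents support:

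- *That the trial plans to test UF unadjusted.* It does not. The error rates above describe a rule that the other sections exclude.
- *That family-wise error could reach 8.5%, the figure for four independent true nulls.* The secondaries are tested only after the primary is met. An exact binomial test with n = 121 then needs at least 60 responders (49.6%; upper tail 0.0204 under 40%, against 0.0313 for 59). A mean UUI change of exactly zero alongside that many 50% reductions would need large offsetting worsening. Three nulls is the realistic worst case.
- *That the rules would disagree 0.5% of the time.* That is only the chance that UF p falls in the window at the planned effect.

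On rounding, the bracketed fractions and the method's name make 0.017 and 0.013 look like display rounding. That is fair, and it keeps this part minor. The declaring sentences still use the decimals alone, and both are rounded in the permissive direction.

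**Conclusion.** The inconsistency is real and is a wording error. Hochberg is the intended rule for UF, and the 0.05 sentence in protocol 14.5.2 is a leftover. Applied literally, and with UF truly null, it would raise family-wise error from 5% to about 8% with three independent true nulls or about 7% under strong correlation. There would be no excess if UF were the only null. These figures rest on assumed correlations and on the equal-variance bound of 0.65. At the planning values the practical risk is negligible. The rounded cut-offs cost at most about 0.1 to 0.2 percentage points, and only with three or four nearly independent true nulls. Study success rests on the primary objective, which neither issue touches.

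**What to change.** In the Performance Requirements of protocol 14.5.2, replace the fixed 0.05 criterion with the sentence used in 14.5.1, 14.5.3 and 14.5.4, which refers the decision to 14.1.3. SAP 7.9.2.2 needs no change.

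As a minor clean-up, use 0.05/3 (as a fraction) and 0.0125 in the sentences of protocol 14.1.3 and SAP 7.5 that declare significance, in place of 0.017 and 0.013.

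The cost is wording only: one protocol sentence and one paragraph in each document. UF power remains 98.3%, the other secondaries stay above 99.9%, and sample size, data collection and the primary test are unchanged.
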